4.5.6.2 Ophthalmologic Examinations

Patients will undergo ophthalmologic examinations at specified timepoints during the study. Patients will be evaluated at screening for risk factors for neurosensory retinal detachment, RVO, or neovascular macular degeneration. Risk factors for RVO include history of serous retinopathy, history of RVO, or evidence of ongoing serous retinopathy or RVO at baseline. Patients with such conditions will be excluded from the study as detailed in Section 4.1.2.

Ophthalmologic examinations will include visual acuity testing, intraocular pressure measurements by tonometry, slit-lamp ophthalmoscopy, indirect ophthalmoscopy, and spectral domain optical coherence tomography (OCT). If spectral domain OCT is not available, time-domain OCT may be performed instead. Ophthalmologic examination must be performed by a qualified ophthalmologist.

4.5.6.3 Cardiac Monitoring

Electrocardiograms

ECG recordings will be obtained at screening and at specified subsequent timepoints, as outlined in the schedule of activities (see [Appendix 1](#)), and may be obtained at unscheduled timepoints as indicated. ECG results will be evaluated by the investigator for determination of eligibility at screening and for the purposes of real-time cardiac safety monitoring and suitability for continued study treatment.

All ECG recordings must be performed using a standard high-quality, high-fidelity digital electrocardiograph machine equipped with computer-based interval measurements. ECGs will be obtained in a standardized fashion as described in the ECG manual. ECGs should be performed with the same machine if possible. Lead placement should be as consistent as possible. ECG recordings must be performed after the patient has been resting in a supine position for at least 10 minutes. All ECGs are to be obtained prior to other procedures scheduled at that same time (e.g., vital sign measurements, blood draws unless pre-authorized by the Medical Monitor) and should not be obtained within 3 hours after any meal. Circumstances that may induce changes in heart rate, including environmental distractions (e.g., television, radio, conversation) should be avoided during the pre-ECG resting period and during ECG recording.

Electronic or paper copies of ECG tracings will be kept as part of the patient's permanent study file at the site.

Guidelines for management of QT prolongation are provided in Section [5.1.3.6](#).

Evaluation of Left Ventricular Function

Patients will undergo evaluation of LVEF, either by ECHO or MUGA, at specified timepoints during the study, and as clinically indicated for new or worsening symptoms. Any patient who develops clinical signs or symptoms suspicious of cardiac failure should undergo an LVEF assessment. Evaluation of left ventricular function must be performed using the same method for each patient.

Guidelines for management of decreased LVEF (asymptomatic and symptomatic) are provided in Section [5.1.2.2](#) and [Table 3](#).

4.5.7 Laboratory, Biomarker, and Other Biological Samples

Samples for the following laboratory tests will be sent to the study site's local laboratory for analysis:

- Hematology: WBC count, RBC count, hemoglobin, hematocrit, platelet count, reticulocyte count, differential count (neutrophils, bands [if available], eosinophils, basophils, monocytes, lymphocytes)
- Chemistry panel (serum or plasma): sodium, potassium, magnesium, chloride, bicarbonate (or total carbon dioxide), BUN or urea, creatinine, albumin, phosphorus, calcium, total bilirubin, ALP, ALT, AST, LDH, CPK, amylase, lipase, glucose (non-fasting)
- Fasting blood glucose (minimum of 8-hour fast), at screening only
- Fasting lipids: total cholesterol, LDL cholesterol, triglycerides (minimum of 8-hour fast), at screening only
- Coagulation: INR, aPTT
- Thyroid function testing: thyroid-stimulating hormone, free triiodothyronine (T3) (or total T3 for sites where free T3 is not performed), free thyroxine

- HIV serology
- HBV serology: HBsAg, hepatitis B surface antibody, total HBcAb
 - If a patient has a negative HBsAg test and a positive total HBcAb test at screening, an HBV DNA test should be performed at screening.
- HCV serology: HCV antibody and (if HCV antibody test is positive) HCV RNA
 - If a patient has a positive HCV antibody test at screening, an HCV RNA test must also be performed to determine if the patient has an active HCV infection.
- Pregnancy test
 - All women of childbearing potential will have a serum pregnancy test at screening, within 7 days prior to initiation of study treatment (i.e., Run-In Day 1). Urine pregnancy tests will be performed on Day 1 of every cycle from Cycle 1. If a urine pregnancy test is not available, serum pregnancy test may be used. If a urine pregnancy test is positive, it must be confirmed by a serum pregnancy test.
 - A woman is considered to be of childbearing potential if she is postmenarcheal, has not reached a postmenopausal state (≥ 12 continuous months of amenorrhea with no identified cause other than menopause), and has not undergone surgical sterilization (removal of ovaries and/or uterus).

[REDACTED]

- [REDACTED]
- [REDACTED]
- [REDACTED]
- [REDACTED]
- [REDACTED]
- [REDACTED]

[REDACTED]

[REDACTED]

**Atezolizumab, Cobimetinib, and Vemurafenib—F. Hoffmann-La Roche Ltd
77/Protocol CO39262, Version 9**

A 5x5 grid of black rectangles on a white background. The rectangles are arranged in a staggered pattern, creating a stepped effect. The top row has 2 rectangles, the second row has 4, the third row has 6, the fourth row has 4, and the bottom row has 2. The rectangles are black with a thin white border.

4.5.8 Patient-Reported Outcomes

To more fully characterize disease burden and clinical benefit of atezolizumab plus cobimetinib and vemurafenib in patients with advanced melanoma, patient-reported outcome (PRO) data will be obtained through use of the following instruments: EORTC QLQ-C30 and the [REDACTED]. The questionnaires will be translated as appropriate in the local language.

To ensure instrument validity and that data standards meet health authority requirements, questionnaires scheduled for administration during a clinic visit will be completed in their entirety by the patient before the patient receives any information on disease status and prior to the performance of non-PRO assessments and the administration of study treatment. Interviewer assessment is allowed but can only be conducted by a member of the clinic staff for patients who are unable to complete the measures on their own. Study personnel should review all questionnaires for completeness before the patient leaves the investigational site.

Patients will use an electronic PRO (ePRO) device to capture PRO data. The ePRO device and/or instructions for completing the PRO questionnaires electronically will be

provided by site staff. The data will be transmitted to a centralized database maintained by the ePRO vendor. The data will be available for access by appropriate study personnel. In the event that the device or the Web-based system is not readily available, paper questionnaires formatted for use as backup data collection forms should be used to minimize missing data. The paper PROs are entered into a Web Portal (i.e., not on the ePRO devices) by the site staff. Compliance with data collection will be documented throughout the study.

To minimize burden to patients and clinical research staff, only the [REDACTED] and select items of the EORTC QLQ-C30 to assess global health status (Questions 29 and 30) and physical functioning (Questions 1–5) and will be administered to patients after treatment discontinuation (due for instance to adverse event, loss of clinical benefit or confirmed disease progression) (see [Appendix 1](#)).

4.5.8.1 EORTC QLQ-C30

The EORTC QLQ-C30 is a validated, reliable self-report measure (Aaronson et al. 1993; Fitzsimmons et al. 1999) (see [Appendix 7](#)) that is commonly used in clinical trials involving patients with metastatic melanoma (Revicki et al. 2012; Schadendorf et al. 2015). It consists of 30 questions that assess five aspects of patient functioning (physical, emotional, role, cognitive, and social), three symptom scales (fatigue, nausea and vomiting, pain), global health/quality of life, and six single items (dyspnea, insomnia, appetite loss, constipation, diarrhea, and financial difficulties) with a recall period of the previous week. Scale scores can be obtained for the multi-item scales. The EORTC QLQ-C30 module takes approximately 10 minutes to complete. A 10-point change is defined as a clinically meaningful difference for the EORTC QLQ-C30 (Osoba et al. 1998).

Atezolizumab, Cobimetinib, and Vemurafenib—F. Hoffmann-La Roche Ltd
79/Protocol CO39262, Version 9

4.6 PATIENT, TREATMENT, STUDY, AND SITE DISCONTINUATION

4.6.1 Patient Discontinuation from Study

Patients have the right to voluntarily withdraw from the study at any time for any reason. In addition, the investigator has the right to withdraw a patient from the study at any time. Reasons for withdrawal from the study may include, but are not limited to, the following:

- Patient withdrawal of consent
- Patient non-compliance, defined as failure to comply with protocol requirements as determined by the investigator or Sponsor
- Study termination or site closure
- Patients who develop a contraindication to atezolizumab therapy during the run-in period, which was not present at randomization and therefore are not eligible to receive atezolizumab, may continue in the study and receive cobimetinib and vemurafenib (960 mg BID). If the condition resolves or improves at a later date, the patient may be eligible to receive atezolizumab following discussion with the Medical Monitor. A week of the vemurafenib/placebo dosing as outlined the run-in period, Days 22–28, would be required prior to starting atezolizumab (see [Table 2](#)).

Every effort should be made to obtain information on patients who withdraw from the study. The primary reason for withdrawal from the study should be documented on the appropriate eCRF. Patients who withdraw from the study will not be replaced.

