5.1.5 Management of Patients Who Experience Specific Adverse Events

5.1.5.1 Dose Modifications during the Run-In Period

Vemurafenib is blinded in this study. Following Days 1–21 of the run-in period, patients in Arm B will receive vemurafenib at a reduced dose (720 mg BID) compared with Arm A (960 mg BID). Thus, dose reductions will be managed via the IWRS system, and dose modifications will differ depending on the arm to which the patient is randomized. See [Table 3](#) for additional details.

During the run-in period (Days 1–28), one dose-level reduction of cobimetinib and vemurafenib is permitted for management of drug-related toxicities. No further dose reductions are permitted in the run-in period. If toxicities do not improve within 28 days following the one level-dose reduction and or treatment interruption for either cobimetinib and or vemurafenib, study treatment should be discontinued, unless resumption of treatment is approved by the Medical Monitor. The run-in period may be extended to a total of 56 days to allow patients to recover from drug-related toxicities prior to proceeding to Cycle 1. Following a dose reduction in the run-in period, no escalation is permitted.

- During the run-in period, the dose of cobimetinib can be reduced by 20 mg QD (one dose level) from 60 mg daily to 40 mg daily during Days 1–21.
- If a vemurafenib dose reduction is required during Days 1–21, the dose of vemurafenib can be reduced from 960 mg BID to 720 mg BID. Patients who are taking 4 tablets from the large bottle during this period should reduce to 3 tablets from the large bottle. From Days 22–28, patients should take vemurafenib 720 mg/matching placebo (two tablets from the large bottle and one from the small bottle) BID.
- If an initial vemurafenib dose reduction to the 720 mg/matching placebo dose is required during Days 22–28, dose reduction will entail a change from dosing with three tablets from the large bottle and one from the small bottle BID to dosing with two tablets from the large bottle and one tablet from the small bottle BID. Drug-related toxicities presenting during Days 22–28 that require a vemurafenib dose reduction should be improving or have resolved (as outlined in Section [5.1.5.3](#) see [Table 3](#)) prior to Cycle 1, Day 1.

Patients must be receiving both study treatments in order to enter the triplet treatment period (Cycle 1, Day 1).

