5.1.5.2 Dose Modifications during the Triplet Treatment Period

There will be no dose modifications for atezolizumab in this study.

The dose of cobimetinib can be reduced by 20 mg QD (one dose level) decrements up to two times for management of drug-related toxicities (i.e., from 60 to 40 mg and then from 40 to 20 mg), except during run-in period when only one dose reduction is allowed. If further dose reduction is indicated after two dose reductions, the patient must

discontinue cobimetinib but may continue treatment with atezolizumab and/or vemurafenib at the investigator's discretion. The dose of cobimetinib may be escalated by a maximum of one dose level (20 mg) from 20 mg QD to 40 mg QD at the investigator's discretion in patients who have previously undergone dose reduction, provided there are no safety concerns. Dose escalation from 40 mg QD to 60 mg QD is not permitted.

The dose of vemurafenib can be reduced by 240 mg/matching placebo BID (one dose level) decrements up to two times for management of drug-related toxicities (i.e., from 960 mg/matching placebo BID to 720 mg/matching placebo BID and then from 720 mg/matching placebo BID to 480 mg/matching placebo BID), except during the run-in period, when only one dose reduction is allowed. If further dose reduction is indicated after two dose reductions, the patient must discontinue vemurafenib but may continue treatment with atezolizumab and/or cobimetinib at the investigator's discretion. The dose of vemurafenib may be escalated by a maximum of one dose level (240 mg/matching placebo dose BID) from 480 mg/matching placebo dose BID to 720 mg/matching placebo BID at the investigator's discretion in patients who have previously undergone dose reduction, provided there are no safety concerns. Dose escalation from 720 mg/matching placebo BID to 960 mg/matching placebo BID is not permitted.

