General guidance for dose modifications and treatment delays and discontinuation	
• The dose of cobimetinib and vemurafenib can be reduced by one dose level in the run-in period (see Section 5.1.5.1).• There will be no dose modifications for atezolizumab.• During the triplet combination period, Cycle 1 and beyond, the dose of cobimetinib can be reduced by 20 mg (one dose level) up to two times (i.e., from 60 mg to 40 mg and then from 40 mg to 20 mg). If further dose reduction is indicated after two dose reductions, the patient must discontinue cobimetinib but may continue treatment with atezolizumab and/or vemurafenib at the investigator's discretion.• During the triplet combination period, in order to preserve the blind, two reductions in tablet number will be allowed in both Arm A and Arm B. The first dose reduction will be from 3 tablets in the large bottle plus 1 tablet in the small bottle BID to 2 tablets in the large bottle plus 1 tablet in the small bottle BID; this will represent a true dose reduction in Arm A (from 960 mg BID to 720 mg BID) and in Arm B (from 720 mg BID to 480 mg BID). If a second dose reduction is required, patients in both arms will reduce from 2 tablets in the large bottle plus 1 tablet in the small bottle BID to 2 tablets in the large bottle BID. This will represent a true dose reduction in Arm A (from 720 mg BID to 480 mg BID) whereas in Arm B, because the small bottle contains placebo tablets, it will represent a "false" dose reduction (with dosing maintained at 480 mg BID). If further dose reduction is indicated after two dose reductions, the patient must discontinue vemurafenib but may continue treatment with atezolizumab and/or cobimetinib at the investigator's discretion.• If atezolizumab is withheld and corticosteroids are initiated for treatment of a toxicity, corticosteroids must be tapered over ≥ 1 month to ≤ 10 mg/day oral prednisone or equivalent before atezolizumab can be resumed. If atezolizumab is withheld for > 12 weeks, the patient should be discontinued from atezolizumab. Study treatment may be withheld for > 12 weeks to allow for patients to taper off corticosteroids prior to resuming treatment. Atezolizumab can be resumed after being withheld for > 12 weeks for patients experiencing clinical benefit as determined by the investigator. The Medical Monitor is available to advise as need.• If either cobimetinib or vemurafenib is withheld for > 28 days because of toxicity, the patient should be discontinued from that drug, unless resumption of treatment is approved by the investigator. The Medical Monitor is available to advise as needed.• After dose reduction, consideration may be given to allow for dose escalation of cobimetinib or vemurafenib by a maximum of one dose level following resolution of the adverse event that resulted in dose modification, provided there are no safety concerns (see Section 5.1.5.2). Escalation is not permitted during the run-in period (see Section 5.1.5.1).

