Pulmonary event, Grade 3 or 4	
Permanently discontinue atezolizumab and contact the Medical Monitor.^{c,d} Withhold cobimetinib and vemurafenib.
Oral or IV broad-spectrum antibiotics should be administered in parallel to the immunosuppressive treatment.Bronchoscopy or BAL with or without transbronchial biopsy is recommended.Initiate treatment with 1–2 mg/kg/day IV methylprednisolone.If event does not improve within 48 hours after initiating corticosteroids, consider adding an immunosuppressive agent.If event resolves to Grade 1 or better, taper corticosteroids over ≥ 1 month.If event resolves to Grade 1 or better within 28 days, cobimetinib and vemurafenib may be resumed with doses reduced by one level. If not, permanently discontinue cobimetinib and vemurafenib.

BAL = bronchoscopic alveolar lavage.

- ^a If corticosteroids have been initiated, they must be tapered over \geq 1 month to \leq 10 mg/day oral prednisone or equivalent before atezolizumab can be resumed.
- ^b Atezolizumab may be withheld for a longer period of time (i.e., $>$ 12 weeks after event onset) to allow for corticosteroids (if initiated) to be reduced to the equivalent of \leq 10 mg/day oral prednisone. The acceptable length of the extended period of time must be based on *the investigator's benefit–risk assessment* and in alignment with the protocol requirements for the duration of treatment and documented by the investigator. The Medical Monitor is available to advise as needed.
- ^c Resumption of atezolizumab may be considered in patients who are deriving benefit and have fully recovered from the immune-mediated event. The decision to re-challenge patients with atezolizumab should be based on *the investigator's benefit–risk assessment* and documented by the investigator. The Medical Monitor is available to advise as needed.
- ^d *In case of pneumonitis, atezolizumab should not be resumed after permanent discontinuation.*

Table 3 Guidelines for Management of Patients Who Experience Specific Adverse Events (cont.)

Event	Action to Be Taken
Endocrine disorders	
Grade 1 hypothyroidism	
• Continue all study treatment.• Initiate treatment with thyroid replacement hormone.• Monitor TSH closely.

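### Section 4.6.1 states vemurafenib 960 mg BID for patients who cannot start atezolizumab, which conflicts with the no-escalation rules for those already reduced, or due a reduction, in the run-in

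*Protocol*

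**What the plan says.** Protocol Section 4.6.1 (Patient Discontinuation from Study) addresses "Patients who develop a contraindication to atezolizumab therapy during the run-in period, which was not present at randomization". Such patients "may continue in the study and receive cobimetinib and vemurafenib (960 mg BID". That is the only vemurafenib dose the section gives for them. It also says that, if the condition later improves and atezolizumab is to start, a week of the Days 22-28 vemurafenib/placebo dosing must come first, with a pointer to Table 2.

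Section 5.1.5.1 (Dose Modifications during the Run-In Period) says "one dose-level reduction of cobimetinib and vemurafenib is permitted for management of drug-related toxicities", and then: "Following a dose reduction in the run-in period, no escalation is permitted". The general row of Table 3 (Section 5.1.5.4) repeats: "Escalation is not permitted during the run-in period".

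Section 5.1.5.2, for the triplet period, adds: "Dose escalation from 720 mg/matching placebo BID to 960 mg/matching placebo BID is not permitted". It does allow one step up at the investigator's discretion, "from 480 mg/matching placebo dose BID to 720 mg/matching placebo BID at the investigator's discretion".

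Table 3 lowers vemurafenib for some events that also hold or stop atezolizumab. In the Grade 3-4 pulmonary row, if the event resolves in time, "cobimetinib and vemurafenib may be resumed with doses reduced by one level".

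**The concern.** Section 4.6.1 is a specific rule for patients with a new safety finding, and it names one dose. Read literally, it takes a patient whose vemurafenib was cut for toxicity in the run-in back to 960 mg BID because atezolizumab can no longer be given. Section 5.1.5.1 says that patient may not be escalated. Nothing states which passage prevails.

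Two things are at stake. The first is safety: the affected patients have a recent toxicity and two possible doses. The second is data quality. The SAP summarizes dose intensity (Section 4.5.1) and adverse events leading to vemurafenib dose reduction (Section 4.5.2), and both would mix two practices if sites read the text differently.

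**Working it through.** No planned sample size, event count or power figure is involved. The check sets the passages side by side and counts active tablets.

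**Inputs**
- One active tablet is 240 mg (Section 4.3.2.3).
- Full dose on Days 1-21 is four active tablets in both arms. On Days 22-28 it is three from the large bottle plus one from the small bottle; the small-bottle tablet is active in Arm A and placebo in Arm B (Table 2).
- Reduced dose on Days 1-21 is three large-bottle tablets. On Days 22-28 it is two large plus one small (Section 5.1.5.1). The general row of Table 3, written for the triplet period, gives this last count as 720 mg BID in Arm A and 480 mg BID in Arm B.

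**Formulae:** active dose per intake = 240 mg × active tablets; gap = 960 − active dose; levels = gap / 240.

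| Patient when the contraindication appears | Active tablets | Active dose per intake (mg) | Gap to 960 (mg) | Levels | Conflict with the no-escalation rules |
|---|---|---|---|---|---|
| Either arm, unreduced, Days 1-21 | 4 | 960 | 0 | 0 | No |
| Arm A, unreduced, Days 22-28 | 4 | 960 | 0 | 0 | No |
| Either arm, reduced, Days 1-21 | 3 | 720 | 240 | 1 | Yes |
| Arm A, reduced count, Days 22-28 | 3 | 720 | 240 | 1 | Yes |
| Arm B, reduced count, Days 22-28 | 2 | 480 | 480 | 2 | Yes |
| Arm B, unreduced, Days 22-28 | 3 | 720 | 240 | 1 | No: planned dose, not a toxicity reduction |

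Per day, 960 mg BID is 2 × 960 = 1920 mg, against 2 × 720 = 1440 mg (ratio 1.33) or 2 × 480 = 960 mg (ratio 2).

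**Patients due a reduction.** Some Table 3 rows hold or stop atezolizumab and also bring vemurafenib back one level lower if the event resolves within 28 days: Grade 3-4 pulmonary events, Grade 2-3 pancreatitis and Grade 3-4 immune-mediated ocular toxicity. If such an event is the contraindication, Table 3 and Section 4.6.1 give different doses for the same patient. Other rows that hold or stop atezolizumab leave vemurafenib unreduced: Grade 2 pulmonary events, adrenal insufficiency, myasthenia gravis or Guillain-Barré syndrome Grades 1-3, and meningoencephalitis. These create no conflict in a patient not otherwise reduced.

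**Lead-in week.** Section 4.6.1 points to the Days 22-28 column of Table 2, which shows only three large plus one small tablet. Section 5.1.5.1 gives reduced patients two large plus one small. A reduced patient who later starts atezolizumab therefore meets a second mismatch.

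**Blinding.** From Day 22, giving 960 mg BID is no change for an unreduced Arm A patient and 240 mg more active drug per intake for an unreduced Arm B patient. Section 4.6.1 names one open dose for both arms and no dispensing mechanism, whereas Sections 4.2 and 5.1.5.1 run dose modifications through the IWRS because the arms differ.

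**The case against.** The best defence is that the passages can be read together. The protocol often states nominal doses without repeating toxicity exceptions: Section 4.3.2.3 has Arm A continuing on 960 mg BID with no carve-out for reduced patients. The next section, 4.6.2, says that patients who must stop one drug for toxicity may continue the others under Section 5.1. The no-escalation rule in Section 5.1.5.1 is unqualified. A careful site could therefore keep a reduced patient reduced. The wording of Section 4.6.1 is also permissive.

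This reading is possible, and that sites would actually diverge is an inference. It does not remove the conflict. The permission concerns continuing; for those who continue, 960 mg BID is the only dose given. The link to Section 5.1 stands in a different section, while Section 4.6.1 is the specific rule and has no such link.

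Three limits on the point do stand, and they rule out stronger readings:
- A reader might infer that every run-in contraindication triggers the conflict, or that Table 3 lowers vemurafenib for all such events. The rows listed above show otherwise, and a contraindication, which Section 4.6.1 does not define, need not be a Table 3 toxicity.
- A reader might infer that an unreduced Arm B patient on Days 22-28 is escalated in breach of Section 5.1.5.2. That bar is written in blinded tablet levels for the triplet period. An unreduced Arm B patient takes three plus one tablets and so is already at the upper level. The rule in Section 5.1.5.1 applies only after a reduction. What remains for this patient is a gap about the blind.
- Some Table 3 rows speak of stopping atezolizumab, which has not yet been given in the run-in, so their application there already needs interpretation.

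**Conclusion.** The conflict is real but confined to a subset: patients who continue after a run-in contraindication to atezolizumab and whose vemurafenib was already reduced, or must be reduced under Table 3 for the contraindicating event. For them Section 4.6.1 contradicts Section 5.1.5.1 and Table 3 by one dose level, or by two for an Arm B patient on the reduced tablet count on Days 22-28. The lead-in week and the handling under the blind are related gaps.

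The number of patients cannot be derived. Multiplying an assumed contraindication rate by the roughly 500 randomized would count everyone with a contraindication, including those with no conflict, and the documents give no such rate. The conclusion rests on the text and tablet counts alone; it assumes nothing about how sites acted and takes no view on which dose is right. It deserves correction because it concerns patients with a fresh safety event, but it does not touch the definition of the primary PFS comparison, which is by randomized arm.

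**What to change.** Reconcile Section 4.6.1 with Sections 5.1.5.1 and 5.1.5.2, Table 2 and Table 3, so that one vemurafenib rule applies to a patient who cannot start atezolizumab. The sponsor's clinical team must choose the rule. The text should cover, explicitly:
- a patient never reduced;
- a patient already reduced, or due a Table 3 reduction for the contraindicating event;
- a patient whose contraindication appears on Days 22-28, in either arm;
- the tablet count for the lead-in week in a patient who was reduced.

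State that the rule is operated through the IWRS in both arms, and move it from the list of reasons for study withdrawal to the dosing sections, with a cross-reference. The cost is amendment wording and an IWRS dispensing rule; no extra patients or data are needed.
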